**Withdrawal of Participants:**

Patients can be taken off the study treatment and/or study at any time at their own request, or they may be withdrawn at the discretion of the investigator for safety, behavioral or administrative reasons. The reason(s) for discontinuation will be documented and may include:

Patient voluntarily withdraws from treatment (follow-up permitted);

Patient withdraws consent (termination of treatment and follow-up);

Patient is unable to comply with protocol requirements.

**Risks to Participants:**

The proposed study poses minimal risks. All potential risks associated with participation in this study will be disclosed in consent documents. Any potential risks that might exist fall into four categories: (a) risks associated with the intervention; (b) risks associated with research assessments, consisting of questions about depression, anxiety, and personal functioning, and other mental and emotional problems; (c) risks associated with potential loss of confidentiality; and (d) risks of worsening mental or emotional state. We address each in turn below.

*Risks of the intervention:* Mobile phone based mental health intervention programs have not been shown to cause any harm.

*Risks associated with research assessments:* Research assessments include questions about depression and other mental and emotional problems. Participants will give voluntary responses to interview questions; they are told that they can decline to answer any questions that they choose. The instruments and methodologies are well tested and are not known to cause problems or distress on the part of the participants. All research interview-based assessments are audio-recorded, for the purpose of review to ensure quality assurance ratings of assessment performance, including ensuring that patients are comfortable with the interview procedures. Audiotapes will be maintained on a secure server with no identifying information in the labels for the duration of the funded study, unless other arrangements are made. On occasion patients may request that audio files be deleted before the end of the study, in which case we will comply.

*Risks associated with potential loss of confidentiality.* There is a slight risk of loss of confidentiality. While transmissions are protected using a Transport Security Layer and communication occurs within a secure messaging platform, there is some possibility that others may see the participant's open webpage or smartphone. Measures to protect security in these instances are described below. Confidentiality may be broken by research staff to ensure the patient's safety if there is an imminent threat to self or others. There is also the remote possibility that research records will be subpoenaed by a court of law. All of these potential losses of confidentiality will be disclosed in the consent documents.

*Risks of worsening mental or emotional state and or self-harm thoughts/events:* Some participants may show a worsening of depressive or anxious symptoms, suicidality or problems during the study period. The development of suicidal ideation during the study remains the most serious risk. However, these are risks inherent in the population and would occur whether or not they were enrolled in the study. It is not believed that the risk of these depressive,

anxious, suicidal, or other adverse outcomes are increased as a function of being enrolled in this study.

All potential risks associated with participation in this study will be disclosed in consent documents.

Antidepressant medications are permissible within this trial. Treatment alternatives outside of the primary care setting include treatment from an outpatient psychiatrist or psychologist, electroconvulsive therapy, or inpatient treatment. The benefits of these alternatives are that they are evidence-based, more intensive and specialized.

**Potential Benefits to Participants:**

The potential benefits of participation are that some participants may receive support for their depression and anxiety. The potential to future patients is that the study may provide fundamentally new and more effective low-intensity treatment approaches that would be more widely available.

**Vulnerable Populations:** n/a

**Setting:**

The PI, [name], has an office within the Center for Behavioral Intervention Technologies (CBITs) within the Northwestern University Department of Preventive Medicine and has access to secure data storage through the Feinberg School of Medicine. The majority of research activities will take place online or on site at the University of Illinois at Chicago (UIC) Counseling Center and at Northern Illinois University (NIU) Counseling & Consultation Services.

The UIC Counseling Center has more than 25 rooms for individual therapies, three group therapy rooms, two or more smaller rooms for self-directed programming (e.g. biofeedback), and three furnished conference/multi-purpose rooms for workshops, staff meetings and gatherings that can each accommodate upwards of 25 people. Counseling Center staff also have access to larger conference spaces in their building and elsewhere on campus. NIU Counseling & Consultation Services operates in a space with 19 individual therapy rooms, a relaxation room (capacity 2-3 people, two group therapy rooms (capacity 10-12 people), and a conference room that can accommodate 20 people.

**Resources Available:**

The PI, [name], is a licensed clinical psychologist and research assistant professor within the Department of Preventive Medicine. [name] has training and expertise in mobile and web-based interventions, and more recently, has begun working on methods to leverage technologies to expand mental health care accessibility for university students. [name] has built strong relationships with the directors of the UIC and NIU counseling centers. The mobile app programmer who is scheduled to work on this project has several years of experience building mobile mental health apps, and has collaborated with researchers from the Center for Behavioral Intervention Technologies for the past 10 years.

Both universities involved in this study have large student bodies, and serve more than 1,000 students per year. Based on the size of these student bodies, it is expected that it will be

feasible to recruit the 68 participants proposed in Phase 1 to conduct user centered design work. In Phase 2, we are interested in assessing the uptake of the intervention program and do not have a set number of participants to recruit.

The PI and a research assistant devote full-time effort to this research project. The PI and research assistant have designated office space within the Center for Behavioral Intervention Technologies, along with a personal computer and have access to a printer and scanner (available software includes SPSS/SAS, MS Office, Adobe, etc.). Both have access to research databases, administrative support, hardware, and software assistance available directly within the Department. The Department has a secure server with data security features ensuring confidentiality of participant data. All laptops are encrypted and the network has firewall protection. In addition, Northwestern University's information technology program supports researchers with the software, hardware, and data storage and retrieval facilities to conduct large-scale projects.

**Prior Approvals:**

Approval will be obtained by the University of Illinois at Chicago and Northern Illinois University prior to commencing research activities.

**Confidentiality:**

Data for all participants will be kept strictly confidential, except as mandated by law. All research files are kept on secure, password protected Northwestern University departmental and medical school servers. All electronic data will be stored on secure servers behind firewalls meeting all security requirements of the medical school. Any paper documentation is kept in locked file cabinets or a locked file room. Participants will be assigned a numerical code for identification in the files. Names and other identifiers will be kept in separate password protected files. Audio data will be stored on secure servers and will only be available for coding by study staff. Online assessments will be conducted on REDCap. This platform uses up to date security measures that are consistent with those used by Electronic Medical Records and are HIPAA compliant. All data collected via the interventions (e.g. mobile application) and assessments are transmitted using Transport Layer Security (TLS) encryption to prevent eavesdropping and tampering information while it is in the transmission pipeline. In addition, all data stored within the intervention is de-identified with a unique key. We will instruct patients on how to add a PIN to their phone to prevent unwanted access. We will clearly inform the patients of the risk of data insecurity. All data presentation will be of aggregate-level data; participants are never individually named.

**Statistical Analysis Plan:**

We used a mixed-methods approach to analyzing the impact of the IntelliCare for College Students program, in that we analyzed quantitative data on app usage and counseling center utilization alongside qualitative data generated through interviews with students and staff.

Demographic data were examined primarily in the form of descriptive statistics, and chi-square tests and a student's t-test were used to examine potential demographic differences between the participants who consented to the study that did (n=117) and did not (n=65) download and register their participant ID to the IntelliCare for College Students app. App usage data were examined in the form of descriptive statistics.

Due to missing data throughout the trial, multiple imputation methods and separate generalized linear mixed models to account for repeated measures from each participant over time, were used to examine symptoms of depression and anxiety at baseline, week 1, week 2, week 4, week 6 and week 8, and anxiety literacy, depression literacy, and cognitive and behavioral coping skills at baseline, month 1 and month 2.

To examine symptom assessments longitudinally, we fit the available weekly symptom assessment data into a structure of baseline, week 1, week 2, week 4, week 6 and week 8 timepoints. Only 2 individuals had complete data. A total of 48 participants only completed the symptom assessment at one time period, 16 (17) completed 2 of the 6 assessments (16 for GAD, 17 for PHQ), 3 (2) completed 3 of the 6 assessments, 5 had 4 of the 6 assessments, and 5 were missing just one assessment. Multiple imputation methods were used to account for missing data. Participants were also prompted to complete measures of our mental health intervention targets on a monthly basis within the app. Many participants did not complete these assessments, and data were examined at baseline, month 1, and month 2. Multiple imputation methods were used to account for missing data.

As originally planned for this project, counseling center utilization data were examined using Simulation Modeling Analysis (SMA) for Time-Series data to determine if there were changes in utilization between the pre-implementation and implementation phases. Because we were unable to enact an enhanced implementation strategy during the second semester of program implementation, we examined implementation as a single phase. SMA evaluates the statistical significance of between-phase changes in data streams and also accounts for the presence of autocorrelation (the non-independence of data points in time-series data streams). A phase effect size (Pearson's R) is produced for each phase-comparison that is then compared to a distribution of data streams, using bootstrapping, resulting in an empirical estimate of the probability of the observed effect occurring by chance.

Interviews were transcribed and coded using a thematic analysis approach. The interview transcripts were first reviewed for thematic content. In creating the codebook, coders met to review their initial codes to reach initial consensus and identified the primary themes that were used to create a codebook. Then, a second round of review took place as the coders reviewed the codebook, refined codes as needed, and completed a final round of coding. The coders met regularly throughout the analytic process to discuss these codes with the study principal investigator, check codes between coders, come to consensus, and ensure validity.

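### Imputing repeated scores before a mixed model adds no stated information and makes the Hypothesis 2 intervals depend on an unnamed imputation routine

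*Combined protocol and SAP*

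**What the plan says.** The Statistical Analysis Plan section states that, because data were missing, "multiple imputation methods and separate generalized linear mixed models to account for repeated measures from each participant over time" were used. The outcomes are depression and anxiety symptoms at six time points, and literacy and coping scores at three.

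Weekly symptom data were placed into a "structure of baseline, week 1, week 2, week 4, week 6 and week 8 timepoints". The section then reports how many of the six scores people supplied:
- "Only 2 individuals had complete data".
- "A total of 48 participants only completed the symptom assessment at one time period".
- For two scores: "16 (17) completed 2 of the 6 assessments (16 for GAD, 17 for PHQ".
- For three: "3 (2) completed 3 of the 6 assessments".
- For four: "5 had 4 of the 6 assessments".
- Five further people lacked a single score.

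On the imputation itself the section says only that "Multiple imputation methods were used to account for missing data". It gives no imputation model, data layout, auxiliary variables, number of imputations or pooling rule. It gives no missingness assumption and no covariance structure for the mixed models. That imputation came before the mixed models is implied, not stated.

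**The concern.** The gaps described are in the repeated outcomes. A mixed model fitted by likelihood uses every observed score and is valid when missingness depends only on observed data, which is the assumption that standard imputation also makes. Imputing the same outcomes from one another, with nothing else described as entering the imputation model, brings in no stated information. It does bring in a second model, estimated from very few people.

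With more than two thirds of the values imputed, the choice of that second model can drive the interval. Hypothesis 2 (Objectives section) concerns reductions in depression and anxiety among users. A reader who does not know the routine cannot tell whether its intervals are too narrow, too wide or about right.

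**Working it through.** The documents give no sample size, interval or precision figure for this analysis, so there is nothing to reproduce. The check has three parts.

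**1. Arithmetic on the stated counts** (Statistical Analysis Plan section)
- People: GAD 48+16+3+5+5+2 = 79; PHQ 48+17+2+5+5+2 = 79. Possible scores: 79×6 = 474.
- Observed GAD scores: 48×1 + 16×2 + 3×3 + 5×4 + 5×5 + 2×6 = 146, so 1 − 146/474 = 69.2% are missing.
- Observed PHQ scores: 48×1 + 17×2 + 2×3 + 5×4 + 5×5 + 2×6 = 145, so 69.4% are missing.
- Two or more scores: 31 people for each measure. Three or more: GAD 3+5+5+2 = 15; PHQ 2+5+5+2 = 14.
- If everyone has a baseline score, each later visit has on average (146 − 79)/5 = 13.4 GAD scores. This is plausible, because the Procedures Involved section has the app prompt both scales at download, but it is not stated.
- Registered users outside the listed categories: 117 − 79 = 38. If all 117 were imputed, 1 − 146/702 = 79% of GAD values would be missing.

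**2. What imputation can add.** Under missing-at-random, the observed-data likelihood averages over the missing scores analytically. Multiple imputation does the same averaging by random draws and pools with Rubin's rules, total variance = W + (1 + 1/m)B. If the imputation model matches the analysis model and has no further variables, the two agree apart from simulation noise. They differ when the imputation model brings in extra variables (none are described) or does not match the analysis model.

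**3. Simulation.** From the documents: 79 people and the GAD pattern 48/16/3/5/5/2. Assumed: normal scores with SD 5, random-intercept truth, intraclass correlation (ICC) 0.4-0.8, data missing completely at random, m = 20. Visit placement is not given in the documents and was varied. There were 200 to 500 replicates per setting (Monte Carlo error about 1 to 1.5 points near 95%). Chained routines work in wide format, regressing each visit on the other five. Predictive mean matching (PMM) used 5 donors. The analysis model throughout is a random-intercept model.

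Coverage of the nominal 95% interval for the week-8 change:

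| Setting | Mixed model, observed data | Compatible random-intercept imputation | Chained normal | Chained PMM |
|---|---|---|---|---|
| Baseline seen, ICC 0.6 | 93.0% | 94.2% | 99.2% | 85.8% |
| Baseline seen, ICC 0.4 | 95.0% | 95.0% | 99.0% | 86.3% |
| Baseline seen, ICC 0.8 | 95.0% | 94.3% | 99.7% | 87.7% |
| Visits at random, ICC 0.6 | 95.3% | 95.3% | 98.3% | 92.3% |
| Monotone dropout, ICC 0.6 | 94.0% | 97.5% | 96.0% | 27.5% |
| Baseline seen, autoregressive truth, correlation 0.4 over 8 weeks | 87.3% | 88.7% | 98.3% | 83.3% |
| Baseline seen, autoregressive truth, correlation 0.7 over 8 weeks | 86.3% | 86.7% | 97.3% | 83.7% |

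Median widths in the first row are 4.30, 4.48, 7.39 and 3.98 points. Chained normal is therefore 7.39/4.30 = 1.7 times the mixed model, and compatible imputation is 4.48/4.30 = 1.04 times. Under monotone dropout only 2 people have a week-8 score, and chained normal imputation is unstable (median width 27.6 against 9.85).

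A separate run with baseline always seen and m = 10 gave about 93% for the mixed model, 86% for PMM and 100% for chained normal, the last with a standard error 1.6 times larger.

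Other assumed variances (intercept SD 4.5, error SD 2.5, slope SD 0 or 0.25 per week, baseline seen, m = 20) kept the ordering: mixed model 92-96%, PMM 76-88%, chained normal 99-100% with a standard error 1.8 to 2.7 times larger. Compatible imputation gave 94.0-95.6%. With m = 5, changing only the seed moved the week-8 estimate by a median of 1.1 points under chained normal imputation and about 0.3 under compatible imputation.

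**The case against.** The strongest reply is that the plan names no routine, so the faults of wide-format chained equations cannot be charged to it. This stands. A reader might infer that the reported intervals are wrong, or that imputing before a mixed model is invalid in itself. The documents support neither: a compatible random-intercept imputation on the same pattern covered 94-97% under the random-intercept truth, with nearly the mixed-model width. It also shows that the best imputation here roughly returns what the simpler analysis gives without it.

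Second, imputation could add information. App-usage and demographic data exist and might have entered the imputation model. Hypothesis 2 is also a mediation hypothesis, and a likelihood fit to the outcome alone does not handle missing mediators used as predictors. Both points stand in principle. The plan describes no auxiliary variables, however, and describes separate models for each outcome, so neither use is documented. They limit the remedy to the analysis of change over time.

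Third, the mixed model is not safe by default. With autoregressive correlation, the random-intercept fit covered only 86-87% for the week-8 change and about 85% for the slope, little better than PMM. This stands, and it is why the fix must state a covariance structure.

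Fourth, Phase 2 is a pilot and the primary outcome in the Procedures Involved section is counseling center utilization. This bears on severity, not on whether the point holds.

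**Conclusion.** The point holds as a should-fix. About 69% of symptom scores are missing. Imputing them with no auxiliary variables described adds no stated information beyond a likelihood mixed model on the observed scores, and it makes every Hypothesis 2 interval for change depend on an unstated routine.

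Depending on that routine, nominal 95% intervals could be about right (compatible multilevel model), too narrow (about 86% coverage with PMM) or too wide (99-100% coverage, about 1.6-1.7 times the width, with chained normal imputation). These figures assume data missing completely at random, baseline always seen, and the variances listed above. Visit placement alone moves PMM coverage from 27.5% to 92.3%.

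The simulations show what can happen, not what did happen in this trial. It would also go too far to say that the wider intervals hide any effect; they lose precision. Whether missing-at-random is itself plausible is a separate question. The primary utilization outcome is not affected.

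**What to change.** Make the main Hypothesis 2 analysis of change over time a mixed model fitted by (restricted) maximum likelihood to the observed symptom, literacy and coping scores, with no prior imputation. State the distribution and a covariance structure that lets correlation decay with time between visits, since a random intercept alone under-covers if correlation is autoregressive. Only 31 people have two or more symptom scores, so also state a simpler fallback if the chosen structure does not converge. The performance of a decaying structure on this pattern was not simulated here.

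Keep multiple imputation as a secondary analysis. Specify a multilevel imputation model compatible with the analysis model, app-usage variables as auxiliaries, the pooling rule, and a number of imputations large enough that changing the seed does not alter the conclusions. If a mediation model is fitted, state separately how missing mediator values are handled.

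The cost is revised SAP wording and a re-run on existing data with a simpler program. The downside is that people with no score on an outcome do not contribute to its main model. Report how many there are, and reconcile the 79 people in the symptom counts with the 117 registered users.

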## Study Protocol:

### Objectives:

This research project aims to develop and test a Student Stress Management (SSM) mobile program, a suite of apps based within the framework of an evidence-based treatment for depression and anxiety that will be integrated within a student health system. This program will improve engagement with mental health services by serving as an access point to mental health treatment options, and providing an opportunity for self-guided treatment. The SSM program will feature components known to be effective both for engagement (symptom assessment and promotion of care accessibility) and treatment (thought restructuring, relaxation exercises, and behavioral activation). Within the suite, students will be prompted to complete symptom assessments on a weekly basis, and those with elevated symptom scores will be provided with feedback and recommendations for on-campus services. All users will be able to access and use interactive treatment apps. The program will be developed with the University of Illinois at Chicago (UIC) and Northern Illinois University (NIU) counseling centers, and will be made available to all UIC and NIU students. These studies will establish a research program that will expand the reach of services and ease the burden of untreated depression and anxiety for college students.

**Phase 1 Aim: Develop the SSM program by refining a mobile smartphone intervention and develop an optimized multi-component implementation strategy using a user-centered design process.** We will start from a suite of apps developed for a general population and, based on needs reported by current students and mental health care providers, they will be optimized for the college student population alongside development of an implementation plan and evaluation metrics. Laboratory-based usability testing and an 8-week field trial will be included as part of the iterative design process to ensure that SSM works optimally both in individual interactions, as well as cumulatively over time.

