**Phase 2 Aim: Conduct a trial of the SSM program within two university communities.** The overall aim of this study is to pilot the SSM program, evaluation metrics, implementation strategies, data collection and assessment procedures for a larger implementation trial. Counseling center utilization will be measured for one academic year to obtain a baseline for both sites. One site will be randomly selected and the SSM program will be implemented, while the other site will continue to collect baseline data. After one academic semester, the additional implementation strategies will be incorporated for an enhanced implementation plan, and both study sites will receive the enhanced implementation plan for one semester. During the implementation phases, counseling center utilization and SSM program use, will be tracked.

**Hypothesis 1:** Introduction of the SSM program will impact utilization of counseling center resources, and the use of an enhanced implementation plan will increase program penetration (e.g., app downloads) and strengthen its impact on utilization. We will explore multiple metrics to assess program impact on utilization, and hypothesize the number of appointments for crisis and follow-up will 1) be reduced during implementation relative to pre-implementation and 2) will be reduced in enhanced implementation relative to initial implementation. We will also explore the impact of implementation on seasonal variations in

counseling center utilization, level of depressive symptoms (as measured by the PHQ-9) at intake, and any other evaluation metrics identified during Phase 1.

**Hypothesis 2:** Sustained use of the SSM program will result in reductions in depression and anxiety among individual users, and these reductions will be mediated by increases in mental health literacy, knowledge of mental health care services, and cognitive and behavioral coping skills.

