### **Procedures Involved:**

Monthly data on engagement with counseling center services will be collected from the counseling center’s Titanium Electronic Medical Record (EMR) to serve as a predeployment “baseline” for Phase 2. For the primary outcome of counseling center resource utilization, we will compare the predeployment phase (the 2 semesters prior to program implementation) to the implementation phases. During the predeployment phase, weekly data will be collected from existing service records at the counseling centers at UIC and NIU on new counseling appointments, follow-up appointment, group therapy appointments and crisis appointments. The data will be reported in aggregate and will not include individual personal identifiers. The SSM program will first be implemented in one study site (UIC or NIU – chosen via random selection) using the initial implementation plan (e.g. advertisements, identification of early adopters, identification of student leaders to serve as champions) designed in Phase 1. Data from individual interviews will be gathered from the first study site will inform an enhanced implementation plan. During this third semester, predeployment data will also be collected at Site #2. Then, the enhanced implementation plan, updated based on the semester 3 deployment at Site #1, will be deployed at both study sites and data will be collected for an additional semester. When the implementation begins on each campus, the program will be made freely available to download, and counseling center intake paperwork will be modified to ask students if they used the SSM program which allows for tracking of counseling center referrals while maintaining patient confidentiality. This design allows us to examine: a predeployment phase for both sites, an initial phase of implementation for Site #1, and an enhanced implementation phase for Site #1 and for Site #2. A strength of this implementation design is that it allows for learning within itself by comparing initial implementation strategies with an enhanced implementation plan. This process of learning and adapting is key for effective and sustainable implementation. Staggering the start times of implementation allows for within-site targeted comparisons of effect of introducing the SSM program on utilization of the counseling center in each site, and for an exploration of between-site differences in the impact of the enhanced implementation plan.

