The study utilizes an interrupted time-series design, which offers a number of benefits over large-N designs and has been shown to be an acceptable approach for examining treatment efficacy as well as a useful design for rigorous implementation research when few sites are

involved. There are both scientific and pragmatic benefits to introducing a program into a system with this design approach. Since these time-series measurements are recorded on a weekly basis, one can observe how change unfolds across time, examine seasonal effects to better evaluate change in these centers that are often at capacity, and investigate the trajectory of change. Because all members of the campus community are granted access to the program, this design meets the needs of community stakeholders.

To examine outcomes for Hypothesis 2 (sustained use of the SSM program will result in reductions in depression and anxiety among individual users, and will be mediated by increases in mental health literacy, knowledge of mental health care services, and cognitive and behavioral coping skills), we will examine longitudinal data from individual users regarding depression and anxiety symptoms, mental health literacy, knowledge and beliefs about mental health care services, barriers to mental health care, and cognitive and behavioral coping skills to determine if sustained program use is associated with changes in these measures.

*SSM Program:* The program will prompt users to complete repeated symptom assessments and provide psychoeducation regarding current symptoms while encouraging students in need to utilize available campus services. Upon download, the Student Hub app will prompt users to complete the PHQ-8 and GAD-7 and will provide feedback on symptoms. Based on symptom scores, users will receive automated feedback about depression/anxiety, availability of mental health and wellness services on campus, and information and interactive digital tools to support continued stress management and wellness. Users will be prompted with ability to use interactive self-help tools within the app suite. Interactive, clinical apps (designed for daily use) are included to facilitate engagement with mood monitoring, and to appeal to a preference for self-reliance.

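### Does the missing rule for week 3, 5 and 7 symptom scores undermine the six-time-point depression and anxiety analysis?

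*Combined protocol and SAP*

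**What the plan says.** The Objectives section sets weekly collection: "students will be prompted to complete symptom assessments on a weekly basis". The Statistical Analysis Plan describes the mapping step in one sentence, "we fit the available weekly symptom assessment data into a structure of baseline, week 1, week 2, week 4, week 6 and week 8 timepoints", and says that multiple imputation and mixed models "were used to examine symptoms of depression and anxiety at baseline, week 1, week 2, week 4, week 6 and week 8".

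It then counts completion out of six. It reports "A total of 48 participants only completed the symptom assessment at one time period" and, at the fuller end, "5 had 4 of the 6 assessments, and 5 were missing just one assessment", with two people complete. Nowhere do the documents give a window for each slot, a tie rule, or a rule for two scores in one slot.

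The analysis addresses Hypothesis 2 ("Sustained use of the SSM program will result in reductions in depression and anxiety among individual users"), for which Procedures Involved promises "we will examine longitudinal data from individual users regarding depression and anxiety symptoms". The same section names a different primary outcome: "For the primary outcome of counseling center resource utilization, we will compare the predeployment phase".

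**The concern.** Nine weekly occasions (0 to 8) go into six slots. The three left over are the only ones equally distant from two slots, so even a nearest-slot convention leaves them undecided. What was done with them affects which cells count as filled, which go to imputation, and who is counted as having a single time point.

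If scores were relabelled, estimates at the affected slots are mis-timed, in a direction set by the unstated rule. If scores were dropped, information was lost from an already sparse data set. A mixed model can take each score at its actual time, so the grid can look like an avoidable cost.

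**Working it through.** The plan states no sample size, power or precision for this analysis, so there is no figure to reproduce. The completion counts come from the Statistical Analysis Plan; everything else is an assumption and is marked as such.

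**1. Filled cells.**
- PHQ: 48×1 + 17×2 + 2×3 + 5×4 + 5×5 + 2×6 = 145.
- GAD: 48×1 + 16×2 + 3×3 + 5×4 + 5×5 + 2×6 = 146.
- Each scale has 79 contributors, so 79×6 = 474 cells. Empty: 329/474 (PHQ) and 328/474 (GAD), about 69%. One time point only: 48/79 = 61%.

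**2. Follow-up scores.** Assume all 79 have a baseline score. Then 145 − 79 = 66 PHQ and 146 − 79 = 67 GAD follow-up scores remain. With equal response across slots (assumed), that is 66/5 = 13.2 PHQ scores per slot. At the same rate, three odd weeks would hold about 3×13.2 = 39.6 scores, so 40 is a natural upper scenario for scores dropped. Even if all 40 went into empty cells, 185/474 = 39% would be filled and 61% would stay empty.

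**3. Relabelling.** Assume steady change and categorical time. If odd-week scores go to the later slot, weeks 4, 6 and 8 hold 39.6 scores. With 20 of them relabelled, 20/39.6 = 0.505 of each slot is one week early.
- Week 8: (8 − 0.505)/8 = 0.937, understated by 6%.
- Week 4: (4 − 0.505)/4 = 0.874, understated by 13%.

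If they go to the earlier slot, week 2 reads (2 + 0.505)/2 = 1.25 (1.26 by simulation), week 4 reads 1.13, and week 8 is unaffected. With 10 scores, all these departures halve. A mixed-model simulation (random intercept, ICC 0.6) agrees with the hand figures to within 0.01.

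In SD units, an assumed true week-8 change of 0.5 SD is 0.5/8 = 0.0625 SD per week. The shift is then 0.505×0.0625 = 0.032 SD at each affected slot. For true changes of 0.25 to 1.0 SD it runs from 0.016 to 0.063 SD.

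**4. Standard error for comparison.** Using baseline and week 8 only, with within-person correlation ρ and scores in SD units, SE = √[(1 − ρ²)/13.2 + (1 − ρ)²/79].
- ρ = 0.6: √(0.64/13.2 + 0.16/79) = 0.225.
- ρ = 0.4: 0.261.
- ρ = 0.8: 0.167.

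Using all six time points, simulation gives 0.215 at ICC 0.6. The 0.032 SD shift is therefore about one seventh of a standard error. An estimate of 0.5 SD would move from 0.5/0.225 = 2.22 standard errors to 0.468/0.225 = 2.08.

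In the extreme where every week-8 entry is really week 7, the understatement is 1/8 = 12.5%, and 2.22 becomes 0.4375/0.225 = 1.94. That could tip only a result already on the border.

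**5. Dropping.** In the same simulation, the variance of a categorical week-8 contrast rises about 0.7% (10 scores dropped), 1.5% (20) and 3-3.5% (40). The last is √1.035 = 1.017, or 1.7% on the standard error.

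**6. What an actual-time fit would gain.** With a separate mean for each week, the gain in week-8 precision is no more than step 5 shows. With a quadratic time curve, the week-8 SE falls from 0.215 to 0.193 with no off-grid scores at all, then to 0.178 (20 scores) or 0.166 (40). The first 0.022 comes purely from the assumed shape. The further 0.015 or 0.027 is available only if that shape is accepted.

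**The case for a change.** The strongest case for a change is that the mapping rule helps define the data set, that the completion counts cannot be reproduced without it, and that only the sponsor can say whether the effect is nil. A count by week and two or three sentences would settle it. Some effects are also larger than those at week 8. If 40 scores were dropped, the variance of a linear slope would rise 34-54%. Under an illustrative decline in response over the slots it would rise roughly 51-73%, and the six-point week-8 SE would be about 0.26 rather than 0.215. Relabelling 20 scores later would pull a linear slope down by about 8%.

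Part of this stands: the rule is not written down, and a reader cannot tell what was done. The larger figures do not carry it further, because they belong to a linear-time model that the plan does not describe. It names six time points. It does not say how time enters the model or that week 8 is the target, so the week-8 and week-4 figures are conditional too.

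An interval reading also fits the text. Data fitted into a structure, with completion counted per time period, suits bins such as weeks 3-4, 5-6 and 7-8. Bins have no ties, and the labels are merely coarser. A fixed grid is also an ordinary choice when missing values are multiply imputed.

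**Conclusion.** No change to the plan is needed. This is an unwritten data-handling convention that analysts fill sensibly, usually with intervals, in a secondary analysis that the plan describes in the past tense as already done. Slot windows and a count of off-grid scores would be useful detail in a results report, but their absence is not a design or analysis fault.

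If time was categorical, the plausible scenarios give a shift of about 0.03 SD from relabelling, or a 3-3.5% rise in week-8 variance from dropping. Both are small against a standard error of roughly 0.16 to 0.26 SD. The alternative is a trade-off, not a correction: it would be post hoc, would need an assumed time shape for nearly all its gain, and would recover no trajectory for the 48 people with one time point.

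This rests on assumptions absent from the documents: a baseline score for all 79, equal response across slots, steady change, an ICC of 0.4 to 0.8, up to 40 off-grid scores, and an available-case model standing in for the imputed one. Merging two scores in one slot was not quantified separately. The week-8 result under earlier assignment also assumes that no week-9 score entered that slot.
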